4.7 Rationale for current trial/Justification of Treatment Options

This is an adaptive trial to assess the safety and immunogenicity of the AZD7442 and SARS-CoV-2 vaccines in patients that are highly immunocompromised against SARS-CoV-2 infection. Adaptation will occur to drive continued recruitment in particular sub-groups to distinguish between the patients who benefit from AZD7442 and those who do not. Improvement in immune responses seen 28 days after administration of AZD7442 will be compared to healthy volunteers in other trials such as the PROVENT clinical trial, and other trials of AZD7442 and SARS-CoV-2 vaccines. Where there is increased variability in the response than the healthy population, analysis will be divided into subgroups to plan extending recruitment.

All participants who consent will be randomised to receive one of the UK approved vaccines currently in deployment to assess the impact of the mAb on response to the vaccine.

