4.7.1 Hypotheses to be tested

1) That treatment with AZD7442 in combination with a SARS-CoV-2 vaccine is safe and well tolerated,

2) That vaccination with a SARS-CoV-2 vaccine does not reduce AZD7442 titres in humans and

3) That AZD7442 in combination with a SARS-CoV-2 vaccine enhances immune responses to SARS-CoV-2.

5 Trial objectives/endpoints and outcome measures

We propose to test the following objectives:

Table 1: Objectives and outcome measures

	Objectives	Outcome measures
Co-Primary	To assess the pharmacokinetics of AZD7442 administered as a single dose of 600 mg IM in immunosuppressed patients	Serum samples will be taken at Day 0 (Predose AZD7442), and days 28, 112 and 180 post AZD7442 treatment and samples shipped to an AstraZeneca approved laboratory for Pharmacokinetics (PK) analysis.
		Samples collected for analyses of AZD7442 serum concentration may also be used to evaluate safety or efficacy aspects related to concerns arising during or after the trial. PK results from the trial will be compared to results from other phase III studies with AZD7442 such as PROVENT.
	To assess the safety and tolerability of a single IM dose of AZD7442, followed by SARS-CoV2 vaccine booster 28 days later with reference to serious adverse events (SAEs) in highly vulnerable patients.	SAE reporting throughout the trial using CTCAE V5.0
	To assess the SARS-CoV-2 specific humoral and cellular immune response against SARS-CoV-2 variants, when a SARS-CoV-2 vaccine is administered 28 days after AZD7442 in patients who are immune suppressed.	The function and magnitude of SARS-CoV-2 specific antibody and T cell responses will be measured at baseline and at additional multiple timepoints after the administration of AZD7442.
		Assays will quantify the amount of serum antibodies to the spike (S) and the nucleocapsid (N) antigens of SARS-CoV-2. This assay will enable the discrimination of antibody responses to SARS-CoV-2 that results from vaccination and/or SARS-CoV- 2 infection. Ab function, including viral neutralisation will be assessed.

		The magnitude and function of SARS-CoV-2 specific T cell responses following the booster vaccination will use assays that give insight into T cell function. Laboratories will measure neutralizing antibodies to SARS-CoV-2 using validated wild-type neutralization assay or pseudo- neutralization assays.

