	To assess the effect of a SARS-CoV-2 vaccine on AZD744 monoclonal antibody titres.	Serum samples will be taken at Day 0 (Predose AZD7442), and days 28, 56, 112 and 180 post AZD7442 treatment and vaccination and samples shipped to an AstraZeneca approved laboratory for quantification of the AZD744 monoclonal Abs generated by therapeutic vaccination, natural infection and vaccinations.
Secondary	The incidence of participants who have a post-treatment response (negative/low at baseline to positive at any time post-baseline) for SARS-CoV-2 nucleocapsid antibodies.	Measurement of SARS-CoV-2 anti NP Abs assessed over the course of the study.
	The incidence of SARS-CoV-2 infection in trial participants.	Self-reported throughout the study duration and assessed at follow up visits.
		Lateral flow testing for SARS-CoV-2 infection in a subset of asymptomatic participants on days 0, 28, 56, 112 and 180. If the lateral flow test is positive for SARS-CoV-2, a nasal PCR swab will be taken to be sent for PCR testing.
		Ad-hoc PCR testing in all symptomatic patients.
		Measurement of SARS-CoV-2 Anti-NP IgG titres
	Sequencing of confirmed SARS-CoV-2 infections to identify SARS-CoV-2 variant and potential AZD7442 escape variants.	Lateral flow testing for SARS-CoV-2 infection in a subset of asymptomatic participants on days 0, 28, 56, 112 and 180. If the lateral flow test is positive for SARS- CoV-2, a nasal PCR swab will be taken to be sent for PCR testing.
		Ad-hoc PCR testing in all symptomatic patients.

	To assess the behaviour of the trial participants before and after trial treatment.	Validated behavioural questionnaire completed by the participants at baseline and at multiple time points over the course of the trial.
	To assess if different SARS-CoV-2 vaccines will preferentially enhance humoral and/or T cell responses in immune suppressed patients receiving AZD7442	Assessment of SARS-CoV-2 humoral and cellular responses in patients randomised to receive different SARS-CoV-2 vaccines
	To assess the severity of SARS-CoV-2 infection contracting COVID-19 within the duration of the trial.	Assessment of SARS-CoV-2 severity in participants contracting COVID-19 within the duration of the trial using the WHO Clinical Progression Scale.
Exploratory	To investigate the mechanism of immunogenicity across disorder/disease treatment across the cohorts.	Immune data will be evaluated within and between disease and treatment cohorts.

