	To identify markers that predict loss/maintenance of AZD7422 titres, response to SARS-CoV-2 vaccines, SARS- CoV-2 infection and adverse events across the cohort.	Immune, clinical and laboratory parameters will be assessed as predictive biomarkers for the primary and secondary trial endpoints.

6 Trial design and setting

The trial is a multicentre, open-label, phase II trial with a randomised comparison of vaccine booster type at 28 days following AZD7442 treatment. Up to 350 patients will be recruited and treated at NHS sites including those already participating in the studies of candidate SARS-CoV-2 vaccines and other interested sites in the UK. Participants will be recruited from groups known to be highly vulnerable to SARS-CoV-2 and therefore likely to benefit from AZD7442 as defined by those recommended as high priority by the Joint Committee on Vaccination and Immunisation (JCVI) (see appendix 1). Patients will be stratified by cohort into 4 groups: Haematological malignancies, Solid tumours, Renal and Hepatic disorders and inflammatory disorders.

All participants will receive AZD7442 treatment followed by vaccination with SARS-CoV2 vaccine booster 28 days later. Immunogenic response will be measured at baseline, throughout treatment and at follow up. The design of the prospective cohort will be initially observational with all participants receiving AZD7442 treatment followed by randomisation to a vaccination with SARS-CoV-2 vaccine booster. The cohorts will be sub divided into subgroups for comparison to healthy volunteers.

Participants will be subdivided into 4 subgroups (see figure 2); up to 120 of these patients enrolled at Oxford University Hospitals NHS site will have additional translational bloods for the additional immunological studies described within the protocol. The Oxford site will decide in conjunction with

the trial management team on which patients from each cohort at the Oxford site will have standard study bloods or translational bloods tests.

Where subjects have conditions that allow entry into more than one cohort of the study then the subject will be allocated into the cohort for the condition that they have had the longest, should that cohort be full, then the subject will be allowed to enter the other cohort for their other condition.

Cohort 1: Haematological malignancies (anticipated 70 participants)

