9.5 Registration and randomisation

Once participants are identified, consented and deemed eligible, they will be assigned a unique trial ID and randomised by the treating team via the same portal. Participants will be randomised to receive one of two boosters in a 1:1 ratio:

Arm 1: Comirnaty bivalent (Original/Omicron BA.1)

Arm 2: Spikevax bivalent (Original/Omicron)

The trial will be unblinded and therefore both the participant and the site research team will know the treatment allocation. The trial pharmacist, research nurse and laboratory team will be notified of the randomisation allocation and trial ID number. A copy of the Randomisation Confirmation, signed Informed Consent Form, and Eligibility Checklist should be filed within the Investigator Site File.

Registration and Randomisation

Patient enrolment for this trial will be through the use of a web-based system: https://trials.cardiff.ac.uk/portal

Details of how to access the system will be supplied to Investigators as part of the trial set-up.

If any problem with the web-based system or it is unavailable, please email the trial team:

[contact]

10 Withdrawal & lost to follow-up

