15.1 Randomisation

Participants will initially be enrolled and registered for the trial and all will receive the trial treatment AZD7442. At 28 days of follow up participants will subsequently be randomised in a 1:1 ratio to one of the two booster vaccines (Spikevax bivalent (Original/Omicron) and Comirnaty bivalent (Original/Omicron BA.1)). A computer-based randomisation allocation process will use random permuted blocks of varying sizes. The trial statistician will produce the randomisation schedule prior to enrolling participants.

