To assess if treatment with AZD7442 followed by a SARS-CoV-2 vaccine 28 days later will increase levels of anti-SARS-COVID-2-anti S-RBD neutralising antibodies in patients. This will be assessed in a hierarchical way firstly comparing age-matched healthy controls from the PROVENT III trial of the AZD7442 and AZD1222 all patients (groups 1, 2, 3 and 4) on both point estimator and variance and if the variance is greater than subdividing into the individual groups by patient group.

Comparisons will be made between each of the vaccines using an ANCOVA model with baseline value as a covariate. An exploratory analysis will be conducted to examine differences between the vaccine types and patient cohorts (see section 16.3 below).

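### Protocol Section 4.7 gives randomisation the purpose of showing how AZD7442 affects vaccine response, but every participant gets AZD7442 and only the booster brand is randomised

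*Protocol*

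**What the plan says.** Section 4.7 closes by giving the reason for randomising participants among the approved vaccines: "currently in deployment to assess the impact of the mAb on response to the vaccine".

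The rest of the Protocol describes a different comparison:

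- Section 6 calls the study a "phase II trial with a randomised comparison of vaccine booster type at 28 days following AZD7442 treatment" and states: "All participants will receive AZD7442 treatment followed by vaccination with SARS-CoV2 vaccine booster 28 days later".
- Section 15.1 repeats this: "Participants will initially be enrolled and registered for the trial and all will receive the trial treatment AZD7442".
- Section 9.5 names the randomised factor: "Participants will be randomised to receive one of two boosters in a 1:1 ratio". The two are Comirnaty bivalent and Spikevax bivalent.
- Section 16.1.2 gives the use of the arms: "Comparisons will be made between each of the vaccines using an ANCOVA model with baseline value as a covariate".
- Table 1 in Section 5 has a matching secondary objective: "To assess if different SARS-CoV-2 vaccines will preferentially enhance humoral and/or T cell responses in immune suppressed patients receiving AZD7442".

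Hypothesis 3 in Section 4.7.1 reads "That AZD7442 in combination with a SARS-CoV-2 vaccine enhances immune responses to SARS-CoV-2". It names no reference condition. Table 1 has a co-primary objective on the reverse effect, that of the vaccine on AZD7442 titres, but none on the effect of AZD7442 on vaccine response.

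**The concern.** Measuring what the antibody does to the vaccine response requires comparable boosted patients with and without the antibody. The randomised arms do not differ in antibody exposure, so Section 4.7 credits randomisation with a property the design lacks.

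The question itself is open. Section 6.1.2 says the effect of AZD7442 on vaccines is unknown and allows that a vaccine may be less effective for up to 9 months to 1 year or more. The same section cites animal data showing no interference and anticipates none. Section 4.6.4 says no clinical study has evaluated AZD7442 combined with boosters. Against that background, and with the purpose stated in Section 4.7, similar responses in the two brand arms could be taken as evidence that AZD7442 does not interfere with vaccination. They would not be such evidence.

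**Working it through.** **1. The planned size.** Section 15.3 uses a difference of 0.5 (log domain), SD 1, 5% significance and 90% power. Section 16.1.1 makes the tests one-sided.

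- Per group: n = 2 × (1.645 + 1.282)² / 0.5² = 68.5, so 69. The Protocol states 70, so the figure reproduces. (Two-sided, it is 85.)
- Four cohorts: 4 × 70 = 280. With 20% loss: 280 / 0.80 = 350.

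This sizes cohort against healthy volunteers. It is not a calculation for antibody against no antibody.

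**2. What the randomised contrast estimates.** Let v1 and v2 be the mean log responses to the two boosters without antibody, and m1 and m2 the changes that prior AZD7442 makes to each.

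- Arm 1 mean: v1 + m1. Arm 2 mean: v2 + m2.
- Difference: (v1 − v2) + (m1 − m2).

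If the antibody effect is common (m1 = m2 = m), it cancels and leaves v1 − v2. For example, halving both responses contributes ln 0.5 − ln 0.5 = 0. If the effect is brand-specific, m1 − m2 remains, but it cannot be separated from an ordinary brand difference v1 − v2. Neither case gives m.

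**3. Whether size could help.** Splitting 280 evaluable participants 140/140 with SD 1, two-sided 5%:

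- Standard error = √(2/140) = 0.1195.
- Power for 0.5: 0.5/0.1195 = 4.18, and 4.18 − 1.96 = 2.22, giving about 99%.
- Detectable at 90% power: (1.960 + 1.282) × 0.1195 = 0.39.

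The brand comparison is well powered. The antibody comparison has 0 participants on one side. For scale only, taking the Protocol's 0.5 and SD 1 as assumptions, a comparison with and without antibody would need 69 (one-sided) to 85 (two-sided) evaluable per group. For a difference of 0.3 this becomes 191 to 234, and for 0.7 it becomes 35 to 43.

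**4. Whether external controls fill the gap.**

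- PROVENT (Sections 4.7, 15.3, 16.1.1): Section 4.5 says its participants were unvaccinated.
- Healthy volunteers from AZD7442 and vaccine-booster trials (Section 6), and controls described by AZD7442 and AZD1222 (Section 16.1.2): these are healthy people, and AZD1222 is neither of the boosters in Section 9.5.
- Other AZD7442 and vaccine trials (Section 4.7): again healthy volunteers, compared on the response 28 days after AZD7442, before the booster is given.

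Section 4.1 documents weaker vaccine responses in immunosuppressed patients without any AZD7442. A gap between trial patients and healthy vaccinees would therefore mix immune status with antibody effect.

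**5. Whether within-participant change fills the gap.** Section 16.1.1 compares baseline with later time points, and the Day 56 outcome in Section 16.1.2 is anti-S-RBD neutralising antibody. AZD7442 itself binds the RBD and neutralises (Section 4.4), so Day 56 against Day 0 rises whatever the vaccine does. Starting from Day 28 removes most of that, but not all. With the half-life of about 90 days in Section 4.6, and assuming first-order decline after Day 28, drug remaining at Day 56 relative to Day 28 is 2^(−28/90) = 0.81. The infused part therefore falls about 19% while the vaccine response develops. T-cell response has no such direct contribution. Either readout describes the response to the booster in the presence of the antibody, not the effect of the antibody on that response.

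**The case against.** The strongest reply is that this is one sentence of rationale. The design statement, the secondary objective and the ANCOVA all describe a comparison of vaccines among AZD7442 recipients, and no listed analysis uses the brand contrast to judge interference. That stands, and it limits the impact.

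Three stronger readings are tempting, and the Protocol does not support them:

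- A reader might infer that hypothesis 3 necessarily needs an antibody-free group. It says the combination enhances responses to SARS-CoV-2, and Section 16.1.1 determines intervention effects against baseline, so a within-participant reading is available. What is missing is the stated reference.
- A reader might infer that no vaccinated control is named. Sections 6 and 16.1.2 do name healthy volunteers from vaccine trials. They are unsuitable for this question, not absent.
- A reader might infer that the randomised test rejects 5% of the time whatever the antibody does. That holds only if the brands are equal and share one antibody effect. The firm statement is that the antibody effect cannot be identified.

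It is also fair to say that part of the remedy is already in place: Table 1 makes T-cell response part of a co-primary outcome, and Day 0, 28 and 56 bloods are scheduled. The reply does not rescue the sentence in Section 4.7. Allocation and exposure are fixed by the Protocol, and no analysis plan can create the missing contrast.

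**Conclusion.** The concern holds. The purpose given to randomisation in Section 4.7 cannot be met: all of the planned 350 participants are to receive AZD7442 and none a booster without it, so the randomised contrast carries no identifiable information on the antibody's effect on vaccine response at any sample size. This follows from the allocation alone and needs no assumption about effect size or variance; exact cancellation, but not the lack of identification, assumes a common antibody effect in both arms. The named external controls do not repair it, because they are not immunosuppressed patients boosted without AZD7442.

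The practical weight is moderate. The error is confined to the rationale, and the risk lies in interpretation. The brand comparison itself is sound and, at 140 per arm under the Protocol's SD of 1, well powered.

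**What to change.** 1. Reword the last sentence of Section 4.7 to say that randomisation compares two boosters given after AZD7442, in line with the existing secondary objective in Table 1.
2. State that the trial does not estimate the effect of AZD7442 on vaccine response, and that no conclusion of no interference will be drawn from the brand contrast.
3. Give hypothesis 3 in Section 4.7.1 a reference: the booster's added effect is the within-participant change from Day 28, sampled before the booster, to Day 56. Keep the humoral outcomes, note that infused AZD7442 contributes to anti-S-RBD neutralisation at both visits, and use T-cell response as the readout that the infused antibody does not supply.

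No new arm, visit or sample is needed, since Section 13.1 already schedules the Day 28 pre-booster and Day 56 bloods. The cost is wording changes and a narrower stated claim.

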4.7.1 Hypotheses to be tested

1) That treatment with AZD7442 in combination with a SARS-CoV-2 vaccine is safe and well tolerated,

2) That vaccination with a SARS-CoV-2 vaccine does not reduce AZD7442 titres in humans and

3) That AZD7442 in combination with a SARS-CoV-2 vaccine enhances immune responses to SARS-CoV-2.

5 Trial objectives/endpoints and outcome measures

We propose to test the following objectives:

Table 1: Objectives and outcome measures

	Objectives	Outcome measures
Co-Primary	To assess the pharmacokinetics of AZD7442 administered as a single dose of 600 mg IM in immunosuppressed patients	Serum samples will be taken at Day 0 (Predose AZD7442), and days 28, 112 and 180 post AZD7442 treatment and samples shipped to an AstraZeneca approved laboratory for Pharmacokinetics (PK) analysis.
		Samples collected for analyses of AZD7442 serum concentration may also be used to evaluate safety or efficacy aspects related to concerns arising during or after the trial. PK results from the trial will be compared to results from other phase III studies with AZD7442 such as PROVENT.
	To assess the safety and tolerability of a single IM dose of AZD7442, followed by SARS-CoV2 vaccine booster 28 days later with reference to serious adverse events (SAEs) in highly vulnerable patients.	SAE reporting throughout the trial using CTCAE V5.0
	To assess the SARS-CoV-2 specific humoral and cellular immune response against SARS-CoV-2 variants, when a SARS-CoV-2 vaccine is administered 28 days after AZD7442 in patients who are immune suppressed.	The function and magnitude of SARS-CoV-2 specific antibody and T cell responses will be measured at baseline and at additional multiple timepoints after the administration of AZD7442.
		Assays will quantify the amount of serum antibodies to the spike (S) and the nucleocapsid (N) antigens of SARS-CoV-2. This assay will enable the discrimination of antibody responses to SARS-CoV-2 that results from vaccination and/or SARS-CoV- 2 infection. Ab function, including viral neutralisation will be assessed.

		The magnitude and function of SARS-CoV-2 specific T cell responses following the booster vaccination will use assays that give insight into T cell function. Laboratories will measure neutralizing antibodies to SARS-CoV-2 using validated wild-type neutralization assay or pseudo- neutralization assays.
	To assess the effect of a SARS-CoV-2 vaccine on AZD744 monoclonal antibody titres.	Serum samples will be taken at Day 0 (Predose AZD7442), and days 28, 56, 112 and 180 post AZD7442 treatment and vaccination and samples shipped to an AstraZeneca approved laboratory for quantification of the AZD744 monoclonal Abs generated by therapeutic vaccination, natural infection and vaccinations.
Secondary	The incidence of participants who have a post-treatment response (negative/low at baseline to positive at any time post-baseline) for SARS-CoV-2 nucleocapsid antibodies.	Measurement of SARS-CoV-2 anti NP Abs assessed over the course of the study.
	The incidence of SARS-CoV-2 infection in trial participants.	Self-reported throughout the study duration and assessed at follow up visits.
		Lateral flow testing for SARS-CoV-2 infection in a subset of asymptomatic participants on days 0, 28, 56, 112 and 180. If the lateral flow test is positive for SARS-CoV-2, a nasal PCR swab will be taken to be sent for PCR testing.
		Ad-hoc PCR testing in all symptomatic patients.
		Measurement of SARS-CoV-2 Anti-NP IgG titres
	Sequencing of confirmed SARS-CoV-2 infections to identify SARS-CoV-2 variant and potential AZD7442 escape variants.	Lateral flow testing for SARS-CoV-2 infection in a subset of asymptomatic participants on days 0, 28, 56, 112 and 180. If the lateral flow test is positive for SARS- CoV-2, a nasal PCR swab will be taken to be sent for PCR testing.
		Ad-hoc PCR testing in all symptomatic patients.

	To assess the behaviour of the trial participants before and after trial treatment.	Validated behavioural questionnaire completed by the participants at baseline and at multiple time points over the course of the trial.
	To assess if different SARS-CoV-2 vaccines will preferentially enhance humoral and/or T cell responses in immune suppressed patients receiving AZD7442	Assessment of SARS-CoV-2 humoral and cellular responses in patients randomised to receive different SARS-CoV-2 vaccines
	To assess the severity of SARS-CoV-2 infection contracting COVID-19 within the duration of the trial.	Assessment of SARS-CoV-2 severity in participants contracting COVID-19 within the duration of the trial using the WHO Clinical Progression Scale.
Exploratory	To investigate the mechanism of immunogenicity across disorder/disease treatment across the cohorts.	Immune data will be evaluated within and between disease and treatment cohorts.
	To identify markers that predict loss/maintenance of AZD7422 titres, response to SARS-CoV-2 vaccines, SARS- CoV-2 infection and adverse events across the cohort.	Immune, clinical and laboratory parameters will be assessed as predictive biomarkers for the primary and secondary trial endpoints.

6 Trial design and setting

The trial is a multicentre, open-label, phase II trial with a randomised comparison of vaccine booster type at 28 days following AZD7442 treatment. Up to 350 patients will be recruited and treated at NHS sites including those already participating in the studies of candidate SARS-CoV-2 vaccines and other interested sites in the UK. Participants will be recruited from groups known to be highly vulnerable to SARS-CoV-2 and therefore likely to benefit from AZD7442 as defined by those recommended as high priority by the Joint Committee on Vaccination and Immunisation (JCVI) (see appendix 1). Patients will be stratified by cohort into 4 groups: Haematological malignancies, Solid tumours, Renal and Hepatic disorders and inflammatory disorders.

All participants will receive AZD7442 treatment followed by vaccination with SARS-CoV2 vaccine booster 28 days later. Immunogenic response will be measured at baseline, throughout treatment and at follow up. The design of the prospective cohort will be initially observational with all participants receiving AZD7442 treatment followed by randomisation to a vaccination with SARS-CoV-2 vaccine booster. The cohorts will be sub divided into subgroups for comparison to healthy volunteers.

Participants will be subdivided into 4 subgroups (see figure 2); up to 120 of these patients enrolled at Oxford University Hospitals NHS site will have additional translational bloods for the additional immunological studies described within the protocol. The Oxford site will decide in conjunction with

the trial management team on which patients from each cohort at the Oxford site will have standard study bloods or translational bloods tests.

Where subjects have conditions that allow entry into more than one cohort of the study then the subject will be allocated into the cohort for the condition that they have had the longest, should that cohort be full, then the subject will be allowed to enter the other cohort for their other condition.

Cohort 1: Haematological malignancies (anticipated 70 participants)

Patients with haematological malignancies and haemopoietic stem cell transplantation will be subdivided into patients receiving active therapy with immunosuppressive or immunomodulating agents (Cohort 1a) and patients receiving aggressive therapy expected to cause temporary ablation of immune function (Cohort 1b).

Cohort 2: Solid tumours (anticipated 70 participants)

The cancer cohorts will be subdivided into the following subgroups for comparison to healthy volunteers:

- Early cancer on systemic treatment (Cohort 2a)
- Advanced cancer on systemic treatment (Cohort 2b)

Cohort 3: Renal and Hepatic disorders (anticipated 70 participants)

Patients with renal (Cohort 3a) and hepatic disorders (Cohort 3b) will be divided into those receiving immunosuppression as part of their treatment, patients with advanced disease for example kidney disease on dialysis, or liver cirrhosis and liver and renal transplantation.

Cohort 4: inflammatory disorders (anticipated 70 participants)

Patients' inflammatory disorders will be divided into those receiving rituximab or not and those receiving other forms of immunosuppressants. Cohort 4a will include participants receiving rituximab and cohort 4b will include participants receiving non-rituximab immunosuppressants.

Each treatment group will then be compared to age-matched healthy volunteers from the mid-2021 phase 1 and 3 trials of AZD7442 and SARS-CoV-2 vaccine booster for both point estimator and variance, and across all patient cohorts.

This will be an adaptive trial that will extend recruitment in any sub-group where more information is required in order to come to a reliable estimator. The immunological assessments will be analysed to allow cohorts to be expanded in case of poor immunogenicity to SARS-CoV-2 or closed if good immunogenicity against SARS-CoV-2 is seen. Recruitment of patients from each group will be limited to ensure the trial captures a representative group of patients from all major immunosuppressive groups most at risk of SARS-CoV-2 mortality. The group sizes will be calculated based on the expected heterogeneity of the group and the degree of variability in the general population.

This may include subdividing groups by disease type in order to gain more homogenous responses. The decision making for these adaptations will be undertaken using a Bayesian partitioning approach adapted from Nugent et al, 2019, details currently under development. The anticipated 70 participants per group is based on expected attrition.

Allowing for an assumed attrition rate of 20% recruitment of 350 participants is anticipated to take 3 months across 4 to 6 sites. Participants will continue on follow up for 6 months.

[figure not shown]

Figure 2: Cohorts and further sub-grouping of immunocompromised participants

Remote data capture will be used (see section 17.1). Samples will be collected both for trial end points and for future research (see section 12 for more information). Participants will be asked to complete questionnaires at the relevant timepoints.

